1. SPECIFIC AIMS

The proposed pilot study is an exploratory implementation and mixed methods evaluation of self-guided repetitive art-making to assess the impact of this artistic practice on 1) self-reported pain levels, 2) self-reported mood states including anxiety and depression, and 3) self-reported feelings of connection for patients living with chronic pain and opioid use disorder (OUD) or documented misuse of opioids. A secondary research focus will be to assess whether viewing art made by patients with chronic pain and OUD/opioid misuse diminishes stigma towards these populations for the broader population.

Aim 1 (Acceptability): Develop three (3) self-guided repetitive artmaking kits for patients with chronic pain and OUD/opioid misuse to use on their own, with instructions in English and Spanish, and train the patients on the use of these artmaking kits through three (3) in-person workshops in English and Spanish. *Hypothesis 1: Simple art kits that offer repetitive artmaking practices will be acceptable for and interesting to patients with chronic pain and OUD/opioid misuse.* Acceptability will be measured by whether patients complete the pre- and post-survey and/or whether they report to the Study Coordinator during monthly check-ins that they have engaged with the art kit(s). At least 80% of patients will report using an art kit on their own (via self-report on surveys, to be supplemented by Study Coordinator text check-ins and storytelling data for patients who participate in the final showcase event). We will ask brief questions at the workshops to assess patients' previous experience with art and openness to mindfulness activities, along with a brief demographic questionnaire, to provide a baseline.

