Aim 2 (Efficacy): Evaluate whether the self-guided repetitive artmaking kits significantly impact patients' self-reported experiences of pain, mood (inclusive of depression and anxiety), and social isolation. *Hypothesis 2: Repetitive artmaking will reduce experiences of pain for patients with both chronic pain and OUD/opioid misuse.* Acceptance criteria: Significant pain reduction during artmaking practice as captured using the first three questions of the BPI Reduced Minus Peg Questions 8-item questionnaire (attached) – questions one and two will be only asked in the pre-survey as these questions ask about pain over the last week and will therefore not change before and after a solo artmaking experience. We also propose to have patients complete the 6-item Pain Catastrophizing Questionnaire (attached) during the in-person workshop to gain an understanding about patients' experiences of pain. This data will be supplemented with qualitative data from the meaning making session and storytelling content, for those who participate. *Hypothesis 3: Repetitive artmaking will reduce depression and anxiety and improve mood for patients with chronic pain and OUD/opioid misuse.* Significance improvements in mood (anxiety and depression) during artmaking practice as captured using single survey questions asking patients to rate their current experiences of anxiety and depression. This data will be supplemented with qualitative data from the meaning making session and storytelling content, for those who participate. *Hypothesis 4: Supporting patients with chronic pain and OUD/opioid misuse in making art will result in higher ratings of social connectivity.* Significant improvement in social connectivity during artmaking practice as captured using the IOS-CC (attached). *Hypothesis 5: Repetitive artmaking will reduce opioid misuse in patients.* Any reduction in non-prescribed opioid use as captured by a question asking patients if they have used non-prescribed opioids in the past 24 hours (modified from the Addiction Severity Index question about recent opioid use) as both a measure of opioid use in connection with artmaking and we will be evaluating patients' opioid use over the course of the study, and a question asking patients to share how high they are at the time of the survey (from the Modified DFAQ-CU Inventory but focusing on opioids not cannabis). This

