3. RESEARCH DESIGN AND METHODS

Overview:

The proposed pilot is an exploratory evaluation of whether repetitive artmaking in home environments is acceptable for chronic pain self-management in individuals with OUD/opioid misuse, and whether self-driven repetitive artmaking can offer respite from pain, depression, and anxiety, and improve social connectivity. The study will recruit approximately 40 individuals living with chronic pain with an OUD diagnosis or opioid misuse from a Montefiore-led methadone clinic, [name]. The Principal Investigators (PIs) will collaborate with an Art Therapist to develop three (3) simple art kits. Patients will participate in an in-person art workshop, to be held in English with the support of a Spanish translator, and complete pre- and post-surveys assessing in-the-moment pain, anxiety, depression, and social connectivity. Patients will be given all three (3) kits to take home and offered financial incentives to complete the same pre- and post-surveys and art kits at home up to four (4) times within a four-month period to assess real-world adoptability and efficacy. The art kits will not include any visible information about Montefiore or the study in the front of the packets; paper versions of the survey will be enclosed within the kits, to support confidentiality. All patients will be invited to a virtual meaning making group to capture qualitative feedback. The study staff will not share the names of patients with anyone outside the core research team – the co-PIs, Study Coordinator, Patient Advocate, Biostatistician, Art Therapist, and Photographer and Exhibit Coordinator. All patients will be invited to have their art photographed and share their experience of the artmaking process and how it relates to their chronic pain and opioid use. Photographs and stories will be shared on the Montefiore campus as an art exhibit, and the layperson audience will be surveyed to assess any resultant alteration in feelings of stigma toward the population of those living with chronic pain and OUD/opioid misuse. Patients who share their artwork will be able to decide if they want their name (or a portion of their name) or a pseudonym to be included in the exhibit alongside their artwork, or if they would like to maintain anonymity.

Implementation:

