At-Home Artmaking: Patients will be invited to take home all three (3) art kits at the end of the in-person workshop, each of which will allow them to make multiple versions of the type of art in question (aka materials for multiple mandalas). Each kit will include multiple copies of the pre- and post-survey assessing pain and mood and a reminder to complete the pre- and post-survey when doing the kits to receive an incentive of \$20 compensation for up to four (4) times within a four-month period (the end date will be included in the art kits). Communication from the Survey Coordinator will also include the links to the pre- and post-surveys. The instructions will prompt patients to complete the survey immediately before starting the art kit and immediately after concluding. Patients will further be prompted to include a photo of their art in the post-survey if they are using the online survey system, or they can text their photo to the Study Coordinator if they have phone-based photography capacity. All instructions will be in English and Spanish. This implementation process is designed to assess real-world use of the art kits.

Data Collection:

Event	Data Collection Method	Measures to be Collected
In-Person Workshop	Patients complete online pre- and post-survey via a QR code or paper form	
 • Questions 1-3 of the BPI Reduced Minus Peg Questions (pre) and question 3 of the BPI Reduced Minus Peg Questions (post) • Pain Catastrophizing Questionnaire • Single question asking about current level of depression • Single question asking about current level of anxiety • IOS-CC • Questions asking about current and recent unprescribed opioid use (pre) and level of highness in the moment (pre, post) • Single question asking about experience with art • Single question asking about openness to mindfulness activities
At-Home Artistic Practice #1	Patients complete paper pre- and post-survey	
 • Questions 1-3 of the BPI Reduced Minus Peg Questions (pre) and

At-Home Artistic Practice #2		question 3 of the BPI Reduced Minus Peg Questions (post) 
 • Single question asking about current level of depression • Single question asking about current level of anxiety • IOS-CC • Questions asking about current and recent unprescribed opioid use (pre) and level of highness in the moment (pre, post)
At-Home Artistic Practice #3		
At-Home Artistic Practice #4		

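### Hypothesis 5: the 24-hour opioid-use item is asked only before each session, so its planned pre/post test cannot be formed; no other contrast is named, and an any-reduction bar could be met by chance

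*Combined protocol and SAP*

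**What the plan says.** Section 1, Aim 2, Hypothesis 5 states its bar as "Any reduction in non-prescribed opioid use as captured by a question asking patients if they have used non-prescribed opioids" in the previous 24 hours. It gives the item two purposes: "as both a measure of opioid use in connection with artmaking", and following patients' "opioid use over the course of the study". A second item, how high the patient is at the moment of the survey, also belongs to Hypothesis 5, and qualitative data supplement both.

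The Data Collection table in Section 3 lists, for the workshop and for each home practice, "Questions asking about current and recent unprescribed opioid use (pre) and level of highness in the moment (pre, post"). The use questions are therefore asked before a session only; the highness rating is asked before and after.

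Data Analysis in Section 3 says that the quantitative analysis will test Hypotheses 2 to 5, will report pre- to post-survey changes on every measure given to patients, and will use paired t-tests, with linear regression for adjusted analyses. It names no exception and no analysis across sessions.

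Hypotheses 2 to 4 are worded in terms of significance, for example "Significant improvement in social connectivity during artmaking practice as captured using the IOS-CC". Hypothesis 5 is not. No significance level is given for any of them.

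**The concern.** Three statements about the same item do not fit together: a schedule with no post-session answer, an analysis built on pre/post change, and a success wording without size, test or reference time. An analyst who follows Data Analysis gets no result for the 24-hour item. An analyst who follows the wording of Hypothesis 5 must choose a comparison after seeing the data, and could then count any fall, however small, as support.

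Aim 2 is labelled as efficacy, and the hypothesis is that artmaking will reduce opioid misuse. A statement to that effect could rest on chance, or on which session was compared.

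**Working it through.** **1. Can the planned change be formed?**

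| Item | Pre | Post | Within-session change |
|---|---|---|---|
| Non-prescribed use, last 24 hours | yes | no | cannot be formed |
| Highness at the moment | yes | yes | can be formed |

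The paired t-test is therefore unavailable for the first item and available for the second.

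**2. Which longitudinal contrasts are possible?** The workshop pre-survey and up to four home pre-surveys carry the item. Section 4 adds a recent-use question at eligibility screening, a further possible baseline. The plan does not say which occasion is the reference, which home session counts, or how zero to four home answers per patient are combined. Home answers exist only when a patient chooses to make art and fills in the survey ("Patients complete paper pre- and post-survey").

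**3. Chance of a net fall with no true change.** The documents give no figure to reproduce, so this is illustrative.

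Inputs:
- Yes/no format, from the wording of Hypothesis 5.
- n pairs (workshop and one named home session): about 40 patients are planned, with high attrition at no stated rate, so n = 20 to 40. The row n = 32 is 80% of 40, echoing "At least 80% of patients will report using an art kit on their own", although that target concerns kit use, not survey completion.
- d, the share of patients whose answer differs between the two occasions: not in the documents; assumed 0.02 to 0.5.

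With D ~ Binomial(n, d) changed answers, and falls given D ~ Binomial(D, 0.5), symmetry gives

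P(more falls than rises) = (1 − P(tie)) / 2.

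Example, n = 40 and d = 0.20: P(tie) = 0.142, so (1 − 0.142)/2 = 0.429.

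| n | d = 0.02 | 0.05 | 0.10 | 0.20 | 0.30 | 0.50 |
|---|---|---|---|---|---|---|
| 20 | 0.153 | 0.271 | 0.350 | 0.399 | 0.418 | 0.437 |
| 25 | 0.179 | 0.298 | 0.368 | 0.410 | 0.427 | 0.444 |
| 32 | 0.210 | 0.326 | 0.385 | 0.420 | 0.436 | 0.450 |
| 40 | 0.240 | 0.348 | 0.398 | 0.429 | 0.442 | 0.456 |

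The range is 27–46% for d from 0.05 to 0.5, and 15–24% at d = 0.02.

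**4. Effect of leaving the session open.** Simulation with a constant use rate: 25 or 40 patients, all answering the workshop and four home surveys; beta-binomial answers with prevalence 0.1, 0.3 or 0.5 and within-patient correlation 0.3 or 0.6 (all assumed); 40,000 runs each. Chance of an apparent fall:
- one named session: about 34–45%
- mean of the four: about 44–48%
- any one of the four: about 61–75%

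**5. What a formal criterion would do.** Exact McNemar on one named pair, two-sided 0.05, no true change: a significant fall occurs at most 1.5% of the time (n = 20 to 40, d = 0.05 to 0.5). Its power for an illustrative fall from 30% to 18%, with correlation 0.3 or 0.6 between occasions, is 9–10% at n = 25 and 21–30% at n = 40.

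**6. Precision.** The approximate 95% half-width for a paired difference near zero is 1.96 × √(d/n). At n = 40, d = 0.2 it is 1.96 × √0.005 = 0.139. At n = 25, d = 0.3 it is 1.96 × √0.012 = 0.215.

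**The case against.** The strongest reply is that the schedule is deliberate. Section 1 says that the first two pain questions are asked beforehand only, because a one-week look-back will not change over a session. A 24-hour look-back fits the same reasoning, and Data Analysis is a general sentence that need not list every exception. This stands as to the schedule: a reader might infer a data-collection mistake, and the documents do not support that. It does not supply an analysis. No exception is written for this item, and the intended longitudinal use has no named contrast.

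Second, any reduction may not be a decision rule. The label for acceptance criteria appears at Hypothesis 2 and is not repeated at Hypothesis 5, and Data Analysis lists Hypothesis 5 among those tested. This stands, so the chance figures are conditional on that reading.

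Third, a reader might infer that Hypothesis 5 as a whole cannot be tested. That goes too far, because the highness rating has its pre/post pair. It measures something different, however, and does not replace recent use.

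Fourth, the percentages are not bounds. They fall with fewer pairs or fewer changed answers, and the any-of-four figure needs every patient to answer all five surveys, which the expected attrition makes unlikely. This stands too.

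Finally, "The proposed pilot is an exploratory evaluation", and opioid use is not among the three outcomes that open Section 1 (pain, mood, connection). This lowers the priority. It also favours descriptive reporting over a success bar.

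**Conclusion.** The point holds in a limited form. For the 24-hour use item, the pre/post change and paired t-test in Data Analysis cannot be formed from the data to be collected, and the plan names no other contrast. This follows from the text and needs no assumption.

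The size is conditional. If any reduction decides Hypothesis 5, and is read as a net fall in users from the workshop to one home session, it is met without true change in about 27–46% of studies over the assumed inputs. The figure is 15–24% if only 2% of patients change their answer, and higher if any of several home sessions may count. Neither prevalence nor discordance is in the documents.

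It should be put right before analysis, at lower priority than matters affecting the main outcomes.

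**What to change.** 1. In Section 3, Data Analysis, state that the 24-hour use item is excluded from the within-session pre/post tests.
2. Name one contrast in advance: the workshop pre-survey against all available home pre-surveys. Use a logistic GEE with a workshop/home indicator, clustered by patient, with a small-sample variance correction and the working correlation fixed beforehand. Report the difference in proportions with its 95% confidence interval, and the number of patients and surveys contributing. State that the screening answer is not the baseline for this contrast.
3. In Hypothesis 5, replace the any-reduction wording with descriptive reporting of that estimate and interval. If a criterion is kept, require the two-sided 95% interval to exclude no change.
4. When reporting, state that home answers come only from artmaking days that patients chose themselves, and that without a control group a change cannot be attributed to artmaking.

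The cost is wording only; no new data are needed. The downsides are real. The interval will be wide (roughly ±14 to ±22 percentage points with one pair per patient, n = 40 to 25), any formal test has low power, and patients without a home survey add no paired information. The setting also differs between a group workshop at the clinic and home, so reporting may differ.

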Check-in Texts & Calls	The Study Coordinator will text all patients one (1) month after the in-person workshop and every one (1) month thereafter for a total of four (4) connection points to assess any barriers to at-home engagement; for those patients who do not respond to texts, the Study Coordinator will complete phone calls and document in Redcap	
 • Question asking whether patients used the art kits in the past month • Documentation of any barriers • Brief qualitative data
Meaning Making Session	All patients will be invited to join a two-hour virtual meaning making session	
 • Rich qualitative data of their experience of the art kits and solo repetitive artmaking
Exhibit	Exhibit viewers (laypersons) will complete an online post-survey via QR code that captures reactions before/after viewing the exhibit	
 • Short set of stigma questions to be developed

Most data will be collected online, via an online survey that automatically populates into a password protected spreadsheet. The Patient Advocate or Study Coordinator will collect all paper surveys during routine treatment at [name] and provide them to the Study Coordinator, who will clean and manually input the data.

Data Analysis:

Analysis will be conducted through a mixed-methods approach. Quantitative analysis to test hypotheses 2-5 will be led by [name], Biostatistician, who will report changes from pre- and post-surveys on all the measures provided to patients and exhibit viewers. For bivariate analyses, he will use paired t-tests. For multivariate analyses, he will employ control variables from baseline, such as demographic variables, and conduct linear regressions. Qualitative analysis to test hypotheses 1-5 will be led by the co-PI, who will code all qualitative data collected from patients (open-ended questions in all surveys, transcript from the meaning making session) to

surface themes that can provide phenomenological or experiential data. Drs. [name] and the co-PIs will collaborate to develop a final report that includes both quantitative and qualitative data.

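### Hypothesis 5 promises to follow non-prescribed opioid use over the study, but after the workshop the question is asked only on days a patient chooses to make art

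*Combined protocol and SAP*

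**What the plan says.** Section 1 (Aim 2, Hypothesis 5) sets the criterion as "Any reduction in non-prescribed opioid use", captured by asking patients "if they have used non-prescribed opioids in the past 24 hours". The item has two purposes: to describe opioid use in connection with artmaking and, separately, "we will be evaluating patients' opioid use over the course of the study". A second item asks how high the patient feels at the time of the survey.

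The Data Collection table in Section 3 lists, for the workshop and for each home session, "Questions asking about current and recent unprescribed opioid use (pre) and level of highness in the moment (pre, post". The use question is therefore pre-survey only, and just the highness rating is repeated afterwards. The At-Home Artmaking paragraph ties home surveys to opening a kit: "The instructions will prompt patients to complete the survey immediately before starting the art kit and immediately after concluding". Sessions are paid "up to four (4) times within a four-month period". The plan sets no dates, no minimum gap and no survey at the end of the period.

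The same table has a check-in row. The Study Coordinator contacts every patient monthly, four times in all, and telephones those who do not answer texts. The listed content is "Question asking whether patients used the art kits in the past month", barriers, and short qualitative comments. No opioid item is listed.

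The Data Analysis paragraph names paired t-tests, and linear regression with baseline control variables. It does not say which occasions are compared for Hypothesis 5, or how the timing of sessions is handled.

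**The concern.** A statement about opioid use across four months needs observations whose timing does not depend on the thing being studied. Here every structured value after the workshop is triggered by the patient's decision to start a kit. That decision may be related to whether the patient used in the past day, in either direction. The workshop, by contrast, is held on a date set by study staff, so a workshop-to-home comparison sets a scheduled day against chosen days.

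Patients who never open a kit at home supply no later value and drop out of any paired comparison, so the result describes only those who engaged. At stake is the across-time half of Hypothesis 5: an apparent reduction could be reported, and would meet the plan's criterion, although use had not changed.

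**Working it through.** **Which comparisons the item allows.** The past-24-hour question is asked before a session and not after it, so it cannot change within a session. The remaining comparisons are workshop against home, or one home session against another. Eligibility screening (Section 4) also asks about recent opioid use, but only before enrolment.

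**How many observations there are.** Inputs: about 40 patients completing a workshop (Section 4), and up to four paid home sessions each (Section 3).
- Workshop: about 40 values.
- Home: 0 to 40 × 4 = 160 values, all on chosen days.
- Follow-up values on dates fixed by the plan: 0.
- Taking four months as about 120 days, four sessions cover 4/120 = 3.3% of days.
- Section 1 aims for at least 80% of patients using a kit on their own. That target can be met with 0.20 × 40 = 8 patients supplying no later value.

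**Size of the bias with no true change.** The documents give no use rate, effect size or significance level, so there is no planned figure to reproduce, and every input below is an assumption. Let p be the share of days on which the answer would be yes, and k how many times likelier a patient is to open a kit on a no-use day than on a use day. The apparent rate on chosen days is

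p / (p + k(1 − p)),

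and its difference from p is p(1 − p)(1 − k) / (p + k(1 − p)).

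For p = 0.40 and k = 2: 0.40/(0.40 + 1.20) = 25%, a spurious fall of 15 points. For k = 0.5 (art likelier on use days): 0.40/(0.40 + 0.30) = 57%, a spurious rise of 17 points. For k = 2 with p = 0.20 the apparent rate is 11%, and with p = 0.60 it is 43%. The difference is zero when p is 0 or 1, so steady users and steady non-users contribute no bias. Only day-to-day variation within a patient does.

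**Allowing patients to differ.** A simulation gave each of 40 patients an individual use rate (beta distribution with mean 0.40, parameters 0.8 and 1.2), one workshop answer and four home answers, with no true change. The paired t-test compared each patient's mean home answer with the workshop answer at a two-sided 5% level, in 4,000 runs per row. The second column is the formula above with one shared rate.

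| k | Shared rate: change | Simulated mean change | Significant fall | Any fall |
|---|---|---|---|---|
| 1 | 0 points | 0 points | 2% | 49% |
| 1.5 | −9 points | −6 points | 13% | 80% |
| 2 | −15 points | −11 points | 30% | 93% |
| 3 | −22 points | −16 points | 60% | 99% |

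With 32 contributors (40 − 8) and one home session each, a significant spurious fall occurred in 8%, 16% and 33% of runs for k = 1.5, 2 and 3. The row for k = 1 shows that, read as any fall in the mean, the criterion is met about half the time with neither change nor selection. The simulation covers choice of day only. It does not model patients whose decision to engage is related to how their use develops.

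**The case against.** The strongest defence is that self-chosen timing is intended. Section 3 says home use is meant to reflect real-world use of the kits, the study is an exploratory pilot, and opioid use is not among the three impacts named at the start of Section 1. The item's first stated purpose, use in connection with artmaking, is well served by surveys at art sessions. This stands for that purpose. It does not supply data for the second purpose, which the plan also states.

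It is also true that the size of the bias is unknown, that steady patterns of use would shrink it, and that change between home sessions could be interpreted if the reasons for choosing a day stayed constant and the same patients supplied every session. The design cannot check either condition.

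A reader might infer several stronger points that the documents do not support:
- That the check-ins collect no outcome. They collect kit use, which serves Hypothesis 1, and qualitative comments that might mention opioids. What is missing is a structured opioid item.
- That patients who make no art are lost altogether. They are still contacted monthly and invited to the meaning making session.
- That evidence of lasting change in weekly pain is undermined. Hypotheses 2 to 4 are judged on change during artmaking, and the plan makes no over-time pain claim.
- That sessions will cluster in the first days. The plan permits this, but it is an extreme case, and monthly contacts may spread sessions out.

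**Conclusion.** The point holds for the across-time part of Hypothesis 5. No structured value of the past-24-hour item after the workshop is independent of the choice to make art, and patients who make none contribute no value. Change from workshop to home sessions therefore cannot be separated from choice of day and loss of non-users without assumptions the data cannot test.

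The bias should not be read as a 15-point fall. That figure needs one use rate shared by all patients, 40% use days, and art twice as likely on no-use days. With spread between patients the same preference gives about 11 points, and the opposite preference gives a rise. The documents support neither direction. The within-session comparisons in Hypotheses 2 to 4, and the pre-post highness rating, are not affected by this point.

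**What to change.** Add the existing past-24-hour question to each of the four monthly check-ins, for every patient whether or not a kit was used. Use a self-completed survey link where possible and the already planned call otherwise, and record which was used. Record the date of every home session. BPI questions 1 and 2 could be added but are optional.

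State in the Data Analysis paragraph that any conclusion about opioid use over the study rests on the workshop baseline against these fixed-date answers, and that home pre-surveys serve only to describe use around art sessions. This would give up to 40 × 4 = 160 follow-up values on a fixed schedule where there are now none. Report the result as uncontrolled change: with no comparison group, it cannot be attributed to artmaking.

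If the item is not added, limit the Hypothesis 5 claim to opioid use around art sessions.

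The cost is a small amendment and slightly longer check-ins, with no new visits or staff. Three downsides should be acknowledged. Some patients will not answer a sensitive question, and Section 6 lists no payment for check-ins. Answers given aloud to the coordinator may differ from those self-completed at the workshop, which could itself look like change. And a link will not suit patients who rely on paper, which is how the Data Collection table lists the home surveys.

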4. STUDY POPULATION

Individuals will be eligible to participate in the pilot study if they:

1. Experience chronic pain
2. Have received medication for OUD in the past 30 days
3. Are aged 18 or older
4. Are fluent in English and/or Spanish

Eligibility screening to be led by the Study Coordinator will include:

1. Chronic pain screening via the first three questions of the BPI Reduced Minus Peg Questions 8-item questionnaire
2. OUD/opioid misuse assessment via the Modified Addiction Severity Index question about recent opioid use

Patients will be enrolled into the study until a total of approximately 40 have completed the in-person art workshops; due to the nature of this community and the high level of attrition, we plan to over-enroll the workshops and as a result may have more than 40 participations at the conclusion.

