5. PARTICIPANT RECRUITMENT

Patients will be recruited by the Study Coordinator and Patient Advocate from [name]. Patient Advocates have existing trusted relationships with clients at this methadone clinic site. The Study Coordinator will coordinate with the Patient Advocate's existing schedule to they can collaborate on talking to patients, sharing information about the study, and in the case of the Study Coordinator, assessing eligibility. Information about the study will additionally be shared in the form of flyers posted around the recruitment site, and the co-PIs will present to all staff during scheduled staff meetings to orient the staff to the project and request direct referrals.

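### Hypothesis 5 credits artmaking with any fall in non-prescribed opioid use over the study, but an effect of patients' OUD medication could not be told apart from it

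*Combined protocol and SAP*

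**What the plan says.** Section 1 (Specific Aims), under the aim labelled efficacy, words Hypothesis 5 causally: "Repetitive artmaking will reduce opioid misuse in patients". Its criterion is "Any reduction in non-prescribed opioid use as captured by a question asking patients if they have used non-prescribed opioids in the past 24 hours", and the same sentence adds that the study will evaluate patients' "opioid use over the course of the study". Hypotheses 2 to 4 ask for a significant change; Hypothesis 5 sets no threshold.

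Section 4 (Study Population), criterion 2, requires that patients "Have received medication for OUD in the past 30 days". It sets no minimum duration or stability. Section 5 (Participant Recruitment) confirms the setting: "Patient Advocates have existing trusted relationships with clients at this methadone clinic site".

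The Data Collection table in Section 3 gives the opioid items, at the workshop and at each home session, as "Questions asking about current and recent unprescribed opioid use (pre) and level of highness in the moment (pre, post". The monthly check-ins hold a "Question asking whether patients used the art kits in the past month", plus barriers and brief qualitative data. Data Analysis in Section 3 plans paired t-tests, and linear regressions with baseline controls for which demographics are the only example. All patients receive the kits, and no comparison group is described.

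**The concern.** Hypothesis 5 attributes a change over four months to artmaking while every patient is under a treatment directed at the same disorder. The plan admits a patient who began that treatment last week and one established for years on equal terms, and it would hold no systematic record of which is which. If use falls, the report could not say whether the kits, the clinic's treatment or both were responsible. If use does not fall, disrupted treatment could be hiding a benefit. A start date that was not collected cannot be recovered reliably once the data are in. The point concerns the comparison across months, not medicine taken between a pre- and a post-survey.

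**Working it through.** The documents give no power, effect size or expected rate for Hypothesis 5, so there is no stated figure to reproduce. The check has four steps.

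**1. What change can the item show?** In the Data Collection table the non-prescribed-use question appears at the pre-survey only; the rating of how high the patient feels appears pre and post. A 24-hour look-back asked once per session cannot show change within that session. It can show only change between sessions, from the workshop to home sessions over up to four months. That is the comparison exposed to background treatment.

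**2. Is the background treatment recorded?** The listed measures are:
- Screening: pain items and a recent-opioid-use question.
- Workshop: demographics, pain catastrophizing, art experience, openness to mindfulness, and the survey items.
- Home surveys: pain, depression, anxiety, IOS-CC, non-prescribed use, highness.
- Check-ins: kit use, barriers, brief qualitative data.

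None asks when OUD medication began or whether it changed, and no chart review is described. The regression could accept time on treatment as a baseline control, but only if it were collected.

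**3. Expected size with no artmaking effect.** Let *s* be the share of recent starters, *f* the fall in their use, *c* the share whose treatment is disrupted and *r* the rise in theirs. Expected overall fall = *s* × *f* − *c* × *r*. All rates below are assumptions; only N = 40 comes from the plan.
- 8 starters, 60% to 30%, other 32 steady at 20%: before, (8 × 0.60 + 32 × 0.20)/40 = 11.2/40 = 28%; after, (8 × 0.30 + 32 × 0.20)/40 = 8.8/40 = 22%. Fall: 0.20 × 30 = 6 points.
- 4 starters: (2.4 + 7.2)/40 = 24%; (1.2 + 7.2)/40 = 21%. Fall: 0.10 × 30 = 3 points.
- No starters: no expected fall.
- 4 starters falling 30 points and 4 disrupted patients rising 30 points: 0.10 × 30 − 0.10 × 30 = 0.
- 4 disrupted patients and no starters: a rise of 3 points.

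**4. How often would any reduction be observed?** A simulation of 200,000 trials took 40 patients, first against last survey, independent responses, stable patients at 30%, and no artmaking effect. The test column is an exact McNemar test with p < 0.05 in the favourable direction.

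| Share of starters | Any reduction, starters 60% to 30% | McNemar | Any reduction, starters 60% to 45% | McNemar |
|---|---|---|---|---|
| 0% | 45% | 1.5% | 45% | 1.5% |
| 10% | 57% | 2.8% | 51% | 2.1% |
| 25% | 73% | 6.6% | 60% | 3.3% |
| 50% | 91% | 20% | 72% | 6.6% |

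The 45% floor is chance: with no threshold, a fall and a rise are equally likely and the rest are ties. Medication adds only the excess over it: at a 10% share, 57 − 45 = 12 points or 51 − 45 = 6 points; at 50%, 91 − 45 = 46 points or 72 − 45 = 27 points. Answers from the same patient would in practice be correlated, which would change these figures.

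**The case against.** A reader might infer that a medication effect will in fact be reported as an artmaking effect. The documents do not support that. They do not exclude recent starters, but they do not say that any will enrol, and they give no share. Nor need the bias favour artmaking: medication stopped or disrupted during four months could raise use. At low shares of starters, most false success would come from the missing threshold and not from medication. These objections stand, and they limit the claim to one about what the data can distinguish.

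The consequence is also limited. The study calls itself an exploratory pilot, and opioid use is not among the three impacts that open Section 1, nor in the opening sentence of Aim 2. That lowers the weight of the point. It does not remove it, because Hypothesis 5 sits under the efficacy aim and is worded as cause and effect.

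The list of measures may be incomplete as seen here: the items of the demographic questionnaire are not shown, and the Addiction Severity Index is attached but not visible, although the protocol uses only a modified question from it. Hence no *listed* measure. Free text at check-ins might mention medication, but incidentally.

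A tempting remedy is to make patients with no medication change the main group for Hypothesis 5. That would select on an event after baseline that can itself respond to opioid use, and could favour those already doing well. A cut at 30 days is also weak: it is an eligibility window, and nothing in the documents shows that treatment effects end there.

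**Conclusion.** The point holds as one of attribution. As planned, an across-study change in non-prescribed use could not be separated into an effect of background OUD treatment and an effect of artmaking, and that change is the only one the use item can show. This follows from the text alone: causal wording, no minimum time on treatment, no comparison group, no listed record of when treatment began, and a pre-session-only item.

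The size and direction are not known. The expected shifts of 3 to 6 points, and the rise from 45% to between 51% and 91% in the chance of any reduction, rest on assumed rates, assumed shares of starters and, for the latter, independent responses. They show that the effect could matter, not that it will. For an exploratory pilot this is an inexpensive improvement worth making before data collection, not a reason to redesign the study.

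**What to change.** 1. Reword Hypothesis 5 and its reporting as uncontrolled change in non-prescribed opioid use during OUD treatment, not as an effect of artmaking. This is the essential part: without a comparison group, no covariate removes every other influence that acts over time.
2. Add one item to the workshop baseline survey asking when current OUD medication began. Ask for the date or approximate time, not a yes/no at 30 days. Use time on treatment as a baseline control in the planned regression, or report Hypothesis 5 descriptively by it; with about 40 patients the split is descriptive only.
3. If medication changes during follow-up are recorded at all, collect them by a confidential route such as the survey enclosed in the kits. A question by text would sit badly with the care that Sections 3 and 7 take to conceal sensitive material. Report such changes descriptively, and do not use them to define the main group for Hypothesis 5.

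The cost is one more survey item and a more modest claim. No visit, arm or clinical procedure changes.
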